1.7 Known Potential Benefits

All patients enrolled in this study would have otherwise undergone CTPA imaging as a part of their usual care. Approximately half of patients enrolled ($n = 300$) will undergo VQ imaging which is associated with a risk of exposure to is comparable and potentially lower than that of CTPA^{50,53,54} but avoids an exposure to iodinated contrast media. Given the significant long-term consequences of even a single episode of CIN,^{11,28} the benefit may be improved methods of identifying patients at risk, and then preventing CIN and subsequent severe outcomes. Published data suggests that VQ may also decrease the risk of hemorrhage from unnecessary exposure to long-term anticoagulant therapy, as a result of over-diagnosis of small subsegmental PE.⁴⁹⁻⁵² At minimum, prior published data clearly demonstrate that the risk of missed VTE with VQ (and selective US) is not increased over CTPA.⁴⁹⁻⁵² Our preliminary data are consistent with published results. In addition, VQ imaging is associated with the same risk of exposure to ionizing radiation as CTPA, but avoids exposure to iodinated contrast media. Thus, patients participating in this study will undergo one of two standard of care imaging studies for PE. Patients who choose not to participate will undergo CTPA testing as planned. Participants will have the opportunity to complete CTPA imaging as planned or undergo VQ imaging, which has the same, or potentially less overall risk than CTPA. All patients will have the opportunity for post-imaging surveillance for AKI, which is not routinely performed. Patients who do develop AKI, based on follow-up creatinine screening at 2-7 days, will have the opportunity to seek follow-up care.

2. Study Objectives

2.1 Primary Objectives

The primary study objective is to compare the incidence of acute kidney injury (AKI) consistent with contrast-induced nephropathy (CIN) in 600 patients with suspected PE and an AKI risk Score ≥ 2 , 300 randomized to CTPA (contrast media exposure) and 300 randomized to VQ (unexposed control) imaging. The primary outcome measure, AKI consistent with CIN. The primary outcome, AKI consistent with CIN, will be defined in both the exposed (CTPA) and un-exposed (VQ) groups using the standard literature definition for CIN:⁶⁹ an increase in creatinine $\geq 25\%$ of baseline or an absolute increase in creatinine of ≥ 0.5 mg/dL ≥ 48 hours and ≤ 168 hours of the enrollment PE imaging study.

Notably, while creatinine remains the clinical standard for identifying AKI of all types, a measurable rise in creatinine may not occur for hours to days after the initial injury. In the case of CIN, the typical peak in creatinine does not occur for 3 to 5 days, with recovery to baseline or new baseline in 7 to 14 days.^{43,44} As with other forms of AKI, in patients with normal or mild impaired renal function, a more severe injury and longer time frame are needed to detect a rise in creatinine indicative of AKI. Indeed, while many studies of CIN limit the follow-up period to 72 hours, this approach may miss 10 to 60% of cases, especially in heterogeneous populations.^{43,91-95} Even using a follow-up method that allows for variable follow-up within a 7 day period, we acknowledge that our study design is also more likely to miss cases rather than over-estimate the incidence of AKI.^{7,20,11} Our goal is to define

the potential to reduce AKI by limiting contrast media exposure. Thus, a prospective, randomized study is required.

We acknowledge that the primary outcome of CIN is likely to occur in patients that remain asymptomatic, as expected for the first stages of AKI. We do plan to measure and report patient-center, symptomatic, severe outcomes (see *Secondary Endpoints*) occurring within 1-year. Aside from our own preliminary data,^{7,11,20} there are no consistent, published, prospective data, with sufficient long-term follow-up,^{32,45} in the emergency care setting, or other comparable heterogeneous, ambulatory population (pre-exposure renal function ranging from normal to impaired). Moreover, there are no prospective, controlled data, in any setting, that can be used to adequately design (and determine the sample size for) a study primarily aimed at measuring the long-term, severe outcomes subsequent to CIN. Hence, we have focused on the first phase of AKI, CIN, as the primary outcome, and plan to use the data to inform future research quantifying the effect of selected contrast media exposure on the prevention of long-term severe outcomes subsequent to the development of CIN.

To determine sample size, we conservatively estimated an overall AKI rate of <20%. The sample size was determined based on a Chi-square test (two-tailed, 5% type I error). A sample size of 188 in the CTPA group (exposed) and 269 in the VQ group (unexposed) in each group will have 80% power to detect an absolute difference of 10%. Assuming up to 5% screening and randomization failures (patients assigned to VQ, but undergo CTPA imaging) and a 30% dropout rate,^{7,11,20,53,89} we will recruit 300 subjects per group. (nQuery 2014; Statistical Solutions©)

Data Analyses Plan: We will select patients with low and moderate risk of PE and a normal chest radiograph. This selection strategy is designed to minimize "crossover" (randomized to VQ/no exposure, but go on to need a CTPA/exposure) (ACR Appropriateness Criteria® <https://www.guideline.gov/popups/printView.aspx?id=35135>, accessed 4/27/2016). Based published literature and our preliminary data, we conservatively anticipate that the crossover rate will be <5% using this selection strategy (see *Preliminary Data and Tables 3 and 4*).⁴⁹⁻⁵² Patients both the CTPA (exposure) and VQ (no exposure) groups will have the same post-test probabilities of PE and the risk of AKI (primary outcome) is not affected by the presence or absence of PE. For all analyses, patients will be considered in the groups to which they are randomly assigned. Statistical significance will be defined by the two-sided p-value <5% (SAS® v 9.1; SAS Institute Inc.).

Baseline Data Analyses: For each of two groups, we will be summarize continuous variables by group using descriptive statistics and categorical variables by frequency counts and percentages. Baseline clinical and demographic data will be compared between two groups to assess the effectiveness of the randomization. Dichotomous and ordinal variables will be examined using chi-square tests and continuous measures with Student's t-tests. Exploratory analysis will be performed to compute p-values which will be presented as an aid to evaluate the overall comparability of the two groups at baseline.

Missing Data Analysis: We anticipate a possible screening and randomization failures (5%)⁴⁹⁻⁵² and dropout (30%)^{7,11,20,53,89} and have adjusted the sample size. It is very unlikely that the dropout mechanism will depend on the unobserved outcome and we will compare the baseline covariates between the dropout and non-dropout groups for substantial differences. Under circumstances where compromise of power may be compromised by missing values, we will use a multiple imputation procedure to make use of all relevant observed data and assume that the data are Missing At Random (MAR), using the SAS® MI and MIANALYZE procedures.

Primary Outcome Analysis: For our primary aim, we will test the following hypothesis:

$$H_0 : |\varepsilon| \geq \delta \quad \text{vs.} \quad H_a : |\varepsilon| < \delta; \text{ where } \varepsilon = P_1 - P_2 \text{ and } \delta = 10\%$$

P_1 and P_2 are the true AKI rates in the CTPA and VQ groups, respectively.

We will reject the null hypothesis and the two groups, CTPA and VQ, will be considered equivalent if

$$\frac{\hat{P}_1 - \hat{P}_2 - \delta}{\sqrt{\hat{P}_1(1 - \hat{P}_1)/n_1 + \hat{P}_2(1 - \hat{P}_2)/n_2}} < -z_{0.05} \quad \text{and} \quad \frac{\hat{P}_1 - \hat{P}_2 + \delta}{\sqrt{\hat{P}_1(1 - \hat{P}_1)/n_1 + \hat{P}_2(1 - \hat{P}_2)/n_2}} > z_{0.05}$$

If we reject the hypothesis of equivalency, we will conduct an analysis for a superior trial. Hence, for comparison with the dichotomous primary outcome, that is, whether a subject develops AKI at the 2-7 day follow-up, a logistic regression model will be used. Group comparisons will be adjusted for baseline covariates. To validate the decision rule in classifying subjects into a low-risk group we will: 1) Measure the AKI rate in the low-risk group (AKIRisk Score <2) with a desired margin of error. We assumed the upper limit of the one-way 95% confidence interval to be <10%, based on preliminary data, and prior literature.^{6,7} as such, we will compute the one-way 95% confidence interval using a Z test statistic; and 2) Compute sensitivity and specificity of the decision rule.

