4.2 Inclusion Criteria

1. Age ≥ 18 years
2. CTPA ordered by the treating provider to evaluate PE.
3. Pre-test probability of PE $\leq 20\%$ (defined using the PE Pretest Consult Score)
4. For randomization to CTPA or VQ imaging: Pre-imaging CIN risk $\geq 20\%$ (AKIrisk Score ≥ 2 points)

- A lower-risk subset of 100 patients (AKIrisk Score <2) will be enrolled and followed. These patients will complete the CTPA as ordered by their provider (not randomized). Data from this lower-risk subset, along with high-risk patients randomized to CTPA will be used will be used to validate the AKIrisk Score, alone and in combination with NGAL and eGFR_{CYS} (Study Aims 1 and 3).

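### The stated 80% power belongs to a superiority chi-square test; the primary 10-point equivalence test has only about 44–60% power at the AKI rates the eligibility rule implies

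*Combined protocol and SAP*

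**What the plan says.** The sample size paragraph of section 2.1 states "The sample size was determined based on a Chi-square test (two-tailed, 5% type I error") and that "A sample size of 188 in the CTPA group (exposed) and 269 in the VQ group (unexposed) in each group will have 80% power". The target is a 10-point difference to be detected, and the only event-rate input is that the investigators "we conservatively estimated an overall AKI rate of <20" per cent. The allowance for losses reads "Assuming up to 5% screening and randomization failures (patients assigned to VQ, but undergo CTPA imaging) and a 30% dropout rate", leading to 300 recruited per group.

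Later in section 2.1, under Primary Outcome Analysis, the hypothesis for the primary aim is H0: |P1 − P2| ≥ 10% against Ha: |P1 − P2| < 10%. The decision rule begins "We will reject the null hypothesis and the two groups, CTPA and VQ, will be considered equivalent if" and requires two z statistics, with unpooled variance, to pass −z(0.05) and z(0.05). The next step is "If we reject the hypothesis of equivalency, we will conduct an analysis for a superior trial", by logistic regression adjusted for baseline covariates.

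On the expected event rate, section 4.2 says "For randomization to CTPA or VQ imaging: Pre-imaging CIN risk" must be at least 20% (AKIrisk Score of 2 or more), and the Précis repeats that threshold. Sections 1.1 and 1.5 give a positive predictive value of 27% for this cut-off, with a 95% CI of 20 to 34% in section 1.5.

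**The concern.** The power statement and the primary test answer different questions. Power to detect a 10-point difference is the chance of a significant result when the arms really differ by 10 points. The primary test succeeds only when the data exclude differences of 10 points in both directions, so the relevant power is the chance of that when the arms are alike. The documents do not give it.

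This bears on the main claim. Section 1.2 states the study hypothesis as contrast avoidance not altering AKI risk, and the results are meant to change imaging practice. If the hypothesis is true and the trial still has a large chance of not showing it, readers should know that beforehand.

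The trigger wording adds to the risk. The plan's null hypothesis is non-equivalence. Missing the criterion means this null was not rejected; it does not reject equivalence. Calling it a rejection invites an inconclusive result to be read as evidence of a difference.

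**Working it through.** **1. The plan's own figure.** Arm-specific rates are not stated. Taking 19% versus 9% (inferred from an overall rate below 20% and a 10-point gap), the two-sided 5% chi-square formula is

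n = [1.960 × √(2p̄(1−p̄)) + 0.842 × √(p1(1−p1) + p2(1−p2))]² / 0.10², with p̄ = 0.14

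This gives 188 per arm, and 188/0.70 = 269. The two printed numbers are therefore best read as 188 evaluable per arm and 269 after 30% dropout. Adding the 5% gives 188/(0.70 × 0.95) = 283, rounded up to 300. The figure is reproducible, and it is a superiority calculation.

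**2. Evaluable patients per arm.** 300 × (1 − 0.05 − 0.30) = 195; 300 × 0.95 × 0.70 = 199.5, taken as 199.

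**3. Event rate.** If equivalence holds exactly, both arms share the CTPA-arm rate. The plan's eligibility rule puts that at 20% or more, and its preliminary data at 27%.

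**4. Power of the specified test at zero difference.**

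SE = √(2p(1−p)/n); power = 2Φ(0.10/SE − 1.645) − 1

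Worked case, n = 199 and p = 0.20: SE = √(0.32/199) = 0.0401; 0.10/0.0401 = 2.494; power = 2Φ(0.849) − 1 = 0.604.

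| Common AKI rate | n = 195 | n = 199 |
|---|---|---|
| 12% | 83.7% | 84.6% |
| 15% | 73.7% | 74.9% |
| 19% | 61.7% | 63.1% |
| 20% | 59.0% | 60.4% |
| 27% | 43.8% | 45.3% |

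Exact enumeration of both binomials with the plan's rule agrees: 59.1% and 60.5% at a 20% rate, 44.2% and 45.7% at 27%.

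**5. Rate at which power is 80%.** Solving 0.10/SE = 1.645 + 1.282 gives a common rate of 13.1% (n = 195) or 13.4% (n = 199).

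**6. Evaluable n for 80% power at a 20% rate.** 2 × 0.16 × (1.645 + 1.282)²/0.01 ≈ 274.1, so 275 per arm.

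**7. What the two-step procedure yields when the arms are identical** (n = 199 per arm, exact, with an unadjusted chi-square standing in for the adjusted logistic model):

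| Common AKI rate | Equivalent | Significant difference | Neither |
|---|---|---|---|
| 20% | 60% | 5% | 34% |
| 27% | 46% | 5% | 49% |

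**The case against.** **The event rate is contestable.** The 20% is a predicted risk attached to a score, and the 27% comes from the contrast-exposed cohort in which the score was derived. The sizing paragraph itself assumes a rate below 20%. Lower figures appear elsewhere: AKI of 8–9% in patients with pre-test VTE risk of 20% or less (section 1.5), an overall rate below 10% (section 2.2, sample size), and 6% in the retrospective VQ group, 86% of whom scored 2 or more (Table 3). At a 10% common rate with 199 per arm, equivalence power would be 91%. It is therefore right that power depends on the rate. But the 8–9% is not restricted to scores of 2 or more, the figure below 10% supports sizing the low-risk cohort, and Table 3 is retrospective with 32% AKI in its CTPA group. Taking the plan's own assumption at 19% still gives only 62–63%.

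**The evaluable number may be higher.** Patients are analysed as randomized, so VQ patients who cross over to CTPA remain in their arm, and dropout alone leaves 300 × 0.70 = 210. Power is then 64% at 20% and 49% at 27%, and the 80% threshold moves to about 14%. This is a fair refinement that does not close the gap. Multiple imputation is planned if missing data compromise power, but no power is claimed for it.

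**The sample size also fits an equivalence test.** The equivalence formula does give 188 per arm at a common rate of 12.5%. The text, however, names a chi-square test to detect a difference, and 12.5% contradicts the eligibility threshold.

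**The trigger wording is only loose.** The formal rule just above it is correct, and a failed equivalence test leads to a further analysis, not a declared difference. That limits the harm, but the sentence still inverts the stated null and no inconclusive outcome is named.

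**Conclusion.** The concern holds. The chi-square arithmetic can be reproduced, but it is attached to the wrong test: the plan's only power figure for the randomized comparison does not describe its primary test. At zero true difference and 5% for each one-sided test, the power of that test is 59–60% at a 20% common AKI rate and 44–45% at 27% with 195–199 evaluable per arm, or 64% and 49% with 210. It reaches 80% only at about 13–14% or below.

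These values assume the eligibility-implied rates apply to both arms, as they must if contrast has no effect, and that losses occur as planned. A real but small difference lowers power: 20% versus 18% gives 57% at 199 per arm. The trigger sentence is wrong as written. Both points must be corrected, because they determine how a failure to show equivalence will be read.

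**What to change.** In section 2.1:

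- State the power of the two one-sided tests, preferably as a short table by common AKI rate and evaluable number. With 195–199 per arm: about 60% at 20%, about 45% at 27%, and 80% only at about 13% or below. A row for 210 per arm would cover the as-randomized reading.
- Label the 80% chi-square figure as power for the follow-on superiority analysis, state the arm-specific rates behind it, and clarify that 188 and 269 are the counts before and after dropout, if that is what was meant.
- Reword the trigger so that the superiority analysis follows when the null hypothesis of non-equivalence is not rejected.
- Define three outcomes in advance: equivalent, different, inconclusive.
- Report the risk difference with 90% and 95% confidence intervals whatever the outcome.

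The cost is protocol and SAP wording, and a less favourable power statement. No patients are added. This discloses the shortfall but does not remove it: 80% power at a 20% rate would need 275 evaluable per arm, or about 414 recruited per arm after the same losses (275/(0.70 × 0.95)).

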The 45-day incidence of VTE in patients with a calculated pre-test risk between 2.5% and 20% was 3%. Importantly, the accepted test threshold prompting imaging for suspected PE is very low: only 2.5%.^{13,48} As such, <15% of patients who underwent imaging for suspected PE ultimately were ultimately diagnosed with VTE. Pre and post-CTPA creatinine data were available for 30% of a validation subset (834 patients from 4 institutions)

[figure not shown]

Figure 3. Example output of the PE PreTest Consult Score (<http://pretestconsult.com/v21/pe>), which allows clinicians to calculate the point-estimate of an individual patient's pre-test probability of pulmonary embolism, at the bedside, using an attribute matching method leveraging over 2 decades of data, from over 8,000 patients evaluated at 7 medical centers, developed by a co-investigator ([name]) along with the PI.^{47,56-59}

[figure not shown]

Figure 2. Cumulative hazard plot for 1-year mortality for patients with and without Contrast-Induced Nephropathy (CIN), adjusted for age and the presence of an active malignancy at the time of enrolment. ($p < 0.01$).

evaluated simultaneously for both suspicion of acute coronary syndromes and PE. In patients at low and moderate risk of PE (pre-test VTE risk $\leq 20\%$), the rate of AKI consistent with CIN, did not differ with the presence (9%) or absence (8%) of a VTE.

The PI has developed methods of risk-stratifying patients for CIN in the emergency care setting: Using data from her contrast-enhanced CT cohort of patients treated in the emergency care setting, the PI evaluated over 100 literature derived risk factors (at varying thresholds) for CIN^{18,23,28,41,60-83} and derived the AKIrisk Score: 2 points for glycosuria on urine dipstick; and 1 point each for Age ≥ 50 years, measured diastolic blood pressure ≥ 100 mmHg, history of HIV or AIDS, and a history of coronary artery disease.⁸ Importantly, an elevated creatinine (SCr), corresponding to an estimated glomerular filtrate rate (eGFR_{SCr}) ≤ 60 ml/min/m²,¹⁷ did not accurately risk-stratify patients for CIN: sensitivity 13%, area under the receiver operating characteristic curve (AUROC) 0.55.^{9,10} In comparison, a AKIrisk Score of ≥ 2 points more accurately predicted CIN: sensitivity 56% (95% CI 43 to 68%), specificity 81% (95% CI 77 to 84%), AUROC of 0.74 (95% CI 0.68 to 0.81) and positive predictive value (27%, 95% CI 20 to 34%).⁸⁻¹⁰ (Figure 4)

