4.4 Randomization

Subjects will be randomly assigned to either the CTPA group or the VQ group (1:1 ratio) using a computer generated randomization list with a block size of 4. Assignment will utilize REDCap (Research Electronic Data Capture, hosted by Indiana CTSI, <https://redcap.uits.iu.edu/>), a secure web-based application that will automate a separate, computer based randomization list for each enrollment site, generated by the biostatistician ([name]). To balance in the risk of PE, we will use the PE PreTest Consult Score as a stratification factor (a <10% risk group and a 10-20% risk group).

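### The sample size sentence gives two different arm sizes "in each group" under a 1:1 design and omits the arm rates; under the plan's own losses, 80% power for a 10-point difference holds only up to a CTPA rate of about 19.6% to 21.0%

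*Combined protocol and SAP*

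**What the plan says.** The sample size paragraph in section 2.1 (Primary Objectives) uses a two-sided 5% chi-square test. On the event rate it says only "we conservatively estimated an overall AKI rate of <20"%, with no rate for either arm. It then states: "A sample size of 188 in the CTPA group (exposed) and 269 in the VQ group (unexposed) in each group will have 80% power" for an absolute difference of 10 points. The allowance for losses reads "Assuming up to 5% screening and randomization failures (patients assigned to VQ, but undergo CTPA imaging) and a 30% dropout rate", and the paragraph ends with 300 recruited per group.

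Other parts of the plan bear on this:

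- Section 2.1 sets the arms as "300 randomized to CTPA (contrast media exposure) and 300 randomized to VQ (unexposed control) imaging".
- Section 4.4 randomises in a "1:1 ratio) using a computer generated randomization list with a block size of 4".
- Section 4.2 requires a predicted risk of at least 20% (AKIrisk Score of 2 or more) for randomisation.
- Section 1.5 reports, for that score threshold in the earlier contrast-CT cohort, a "positive predictive value (27%, 95% CI 20 to 34"%).
- The Data Analyses Plan in section 2.1 says: "For all analyses, patients will be considered in the groups to which they are randomly assigned".
- The primary hypothesis in section 2.1 is equivalence within 10 points. The difference test is the fallback if equivalence is not shown.

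**The concern.** The sentence assigns one number to CTPA and another to VQ, then says both apply to each group. Nothing in the plan provides for unequal arms. If 269 evaluable VQ patients really were needed, 300 per arm less 30% dropout would leave 210 and miss the requirement.

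The design rate is also hard to place. An overall rate below 20% is assumed for patients who must have a predicted risk of at least 20% to be randomised, and the text does not say whether it refers to CTPA, VQ or both arms pooled. In this range, a fixed absolute difference needs more patients as the rates rise, so the power statement depends on the missing figures.

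This is the plan's only power statement for the randomised comparison. As written, an ethics committee, the monitoring board or a later reader cannot reconstruct what 300 per arm rests on.

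**Working it through.** **Inputs.** From section 2.1: two-sided alpha 0.05, 80% power, 10-point difference, 30% dropout, 5% failures, 300 per arm. From section 4.4: 1:1 allocation. The arm rates are not in the plan, so they are varied below.

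**Formula.** Per group, with p̄ = (p1 + p2)/2:

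n = [1.96 × √(2p̄(1 − p̄)) + 0.8416 × √(p1(1 − p1) + p2(1 − p2))]² / (p1 − p2)²

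There is no continuity correction. Power uses the same pooled-variance test.

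**Step 1: reproduce 188 and 269.**

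- 19% vs 9%: n = 187.8, so 188. This matches.
- 188/0.70 = 268.6, so 269. This matches, using the paragraph's own dropout rate.
- A rival origin exists: 27% vs 17% gives n = 268.2, also 269. That would make 269 an evaluable number, needing 269/0.70 = 384.3, so 385 per arm. It does not fit 300, and its average rate of 22% does not fit an overall rate below 20%.
- Read literally, 188 CTPA and 269 VQ give 84.6% power at 20% vs 10%. They give 80% only near 22.5% vs 12.5%.

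**Step 2: which pair leads to 300?**

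- 20% vs 10%: n = 198.96, so 199. Then 199/(0.70 × 0.95) = 299.2, so 300.
- 19% vs 9%: 188/(0.70 × 0.95) = 282.7, so 283.
- If the losses are added instead (35%), the results are 199/0.65 = 306.2, so 307, and 188/0.65 = 289.2, so 290.

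The compounded calculation at 20% vs 10% hits the target exactly, but 188 itself belongs to 19% vs 9%. The text does not settle which pair was used.

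**Step 3: evaluable numbers that 300 per arm yields.** With losses added, 300 × 0.65 = 195. With losses compounded, 300 × 0.70 × 0.95 = 199.5. With dropout only, 300 × 0.70 = 210.

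**Step 4: power with equal arms.**

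| CTPA vs VQ | 195 per arm | 199.5 per arm | 210 per arm |
|---|---|---|---|
| 19% vs 9% | 81.5% | 82.3% | 84.2% |
| 20% vs 10% | 79.2% | 80.1% | 82.1% |
| 25% vs 15% | 69.6% | 70.6% | 72.8% |
| 27% vs 17% | 66.5% | 67.5% | 69.8% |
| 27% vs 15% | 83.1% | 84.0% | 85.8% |

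The highest CTPA rate that keeps 80% power for 10 points is 19.6% (195), about 20.0% (199.5) and 21.0% (210).

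**Step 5: crossover.** Patients are analysed as randomised, so a VQ patient who goes on to CTPA stays in the VQ arm. If a share c of that arm takes the CTPA rate, the VQ rate becomes p2 + c(p1 − p2). With c = 5% and 210 per arm, power is 79.8% at 19% vs 9%, 77.5% at 20% vs 10%, 67.9% at 25% vs 15% and 64.9% at 27% vs 17%.

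**The case against.** The strongest reply is that this is a drafting slip and the target of 300 is sound. At 20% vs 10%, compounding both stated losses reproduces 300 exactly and leaves 80.1% power. That stands. A reader might infer that the trial recruits too few patients, or that 385 per arm are needed. The plan does not support this, because it would require 269 to be an evaluable number. Nor should 188 be treated as the number that 300 per arm will yield: 188 of 300 is a 37% loss (1 − 188/300), more than the plan assumes.

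A second reply is that 27% vs 17% is a harsh scenario. This also stands in part. The 27% comes from an earlier contrast-CT cohort and is not a declared design rate. The scenario assumes the full 30% dropout: at 20% dropout (240 per arm) power is 75.5%, and with no dropout 84.2%. It also assumes a difference far below the plan's own retrospective comparison of 32% vs 6% (section 1.5, Table 3), at which power is close to 100%. Lower AKI rates appear in section 1.5 as well (15% after CTPA; 8% to 9% at low or moderate PE risk), though those groups were not selected on the AKIrisk Score.

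A third reply concerns the word conservatively. A reader might call it wrong, since lower rates need fewer patients. But planning at the top of a range below 20% is conservative within that range, so removing the word is a matter of preference.

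Finally, whether crossovers stay in their assigned arm is already settled by the as-randomised rule. What remains is that the sample size paragraph treats them only as a loss to inflate for.

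**Conclusion.** The sentence is wrong as written. It contradicts itself, the 1:1 allocation and the 300 per arm, and it most likely shows a dropout-inflated recruitment figure as an evaluable arm size. That origin is an inference; only the sponsor can confirm it and the intended pair of rates.

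Under the plan's own losses, 80% power for a 10-point difference is reached up to a CTPA rate of about 19.6% to 21.0%, close to the lowest predicted risk that admits a patient to randomisation. Above that it falls to roughly 70% to 73% at 25% vs 15% and 66.5% to 69.8% at 27% vs 17%. It is higher if dropout is below 30% or the difference exceeds 10 points.

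These figures rest on an uncorrected, unadjusted chi-square test and, in the Step 4 table, on no dilution by crossover. They approximate the fallback difference test, which the plan carries out as covariate-adjusted logistic regression. They say nothing about power for the primary equivalence test. A reader might infer that the trial is underpowered; the documents support only that its power statement cannot be reconstructed and holds near the lower end of the eligible risk range. This should be fixed.

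**What to change.** Replace the sentence with one evaluable number per group, the rate in each arm as confirmed by the sponsor, and the inflation step by step. For example: *With 199 evaluable subjects per group, a two-sided 5% chi-square test has 80% power for 20% (CTPA) vs 10% (VQ); allowing for 30% dropout and 5% failures, 300 per group will be recruited.* If 19% vs 9% was intended, the figures are 188 evaluable, 269 after 30% dropout and 283 after both losses.

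In the same paragraph:

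- Say which arm the rate below 20% refers to.
- Add the power at 25% vs 15% and 27% vs 17%.
- State that patients who cross from VQ to CTPA, analysed as randomised, dilute the difference rather than reduce the number analysed, and give the power with 5% crossover. If the 5% step stays in the inflation, say which failures it covers.
- State that these are approximate figures for the fallback difference test, not for the equivalence test.

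This costs a wording change and no added enrolment. The downside is that the stated power looks slightly less favourable at higher AKI rates.

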4.5 Moment of Enrollment

Enrollment occurs when the consent form is signed and dated, randomization is complete, and the subject completes the study-assigned PE imaging study.

5. Study Procedures

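### The 10-point equivalence test is planned only as randomised; VQ-to-CTPA crossover tilts any conclusion about contrast exposure slightly towards equivalence, and no supportive exposure analysis is specified

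*Combined protocol and SAP*

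**What the plan says.** Section 2.1 (Primary Outcome Analysis) sets the null hypothesis as an absolute difference in AKI rate of 10 points or more. It gives two one-sided z conditions, each at 5%: "We will reject the null hypothesis and the two groups, CTPA and VQ, will be considered equivalent if" both are met. If equivalence is not shown, a superiority analysis by logistic regression follows.

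The Data Analyses Plan in the same section fixes one grouping rule: "For all analyses, patients will be considered in the groups to which they are randomly assigned". It describes crossover as a patient randomised to VQ who then needs CTPA, and says "we conservatively anticipate that the crossover rate will be <5" percent. The sample-size paragraph allows up to 5% for such patients and 30% for dropout. Section 6.0 sends to CTPA only patients with an intermediate-risk VQ and a negative leg ultrasound. Section 1.5 reports 3% intermediate VQ studies in the preliminary series.

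No section plans a per-protocol, as-treated or complier analysis of the primary endpoint, or names a crossover level at which an equivalence result would be qualified.

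Section 4.5 says enrolment occurs when consent is signed, randomisation is done and "the subject completes the study-assigned PE imaging study".

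**The concern.** Analysing as randomised is conservative for a test of difference, because non-adherence pulls the arms together. In an equivalence test the same pull favours the conclusion being sought. Here all the foreseen crossover runs from unexposed to exposed, so it can only shrink the contrast in exposure.

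This matters because the protocol wants to speak about exposure as well as imaging strategy. Section 1.2 promises to quantify the AKI risk from contrast media, and section 2.1 labels the arms as exposure and no exposure. A finding of equivalence would probably be read as saying that contrast does not cause AKI, yet the only planned analysis is slightly biased towards that reading. The 5% allowance in the sample size protects power to detect a difference. It does not protect the error rate of the equivalence claim.

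**Working it through.** **The plan's own sample size.** "The sample size was determined based on a Chi-square test (two-tailed, 5% type I error"), with 80% power for a 10-point difference and an overall AKI rate below 20%. The arm rates are not given. If 19% and 9% are assumed, the pooled-variance formula gives

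n = [1.96 √(2 × 0.14 × 0.86) + 0.842 √(0.19 × 0.81 + 0.09 × 0.91)]² / 0.10² = (0.962 + 0.409)² / 0.01 ≈ 188 per arm.

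Then 188 / 0.70 = 268.6, or 269, and 269 / 0.95² = 298, close to the 300 recruited. So 188 and 269 reproduce as one per-arm number before and after dropout. Read literally as unequal arm sizes at 20% vs 10%, they give 84.6% power, not 80%. This calculation concerns a difference and says nothing about equivalence error.

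**Inputs for the check.**
- Margin 10 points, two one-sided tests at z = 1.645, unpooled standard error (section 2.1).
- Evaluable patients per arm: 300 × 0.95 × 0.70 = 199.5, taken as 199 (assumption from the plan's allowances).
- Crossover c: 0%, 3% (intermediate VQ rate, section 1.5) and 5% (ceiling, section 2.1).
- Arm rates (assumed): 20% vs 10%, 15% vs 5%, and 27% vs 17%. The last uses the 27% positive predictive value reported for an AKIrisk Score of 2 or more.
- Patients who cross over have the same AKI risk and the same contrast effect as the rest (assumption).

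**Dilution.** Observed VQ rate = p₂ + c(p₁ - p₂), so the as-randomised difference = (1 - c)(p₁ - p₂). At c = 5%, a true 10.0 points appears as 9.5.

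**One case by hand.** For 20% vs 10% and c = 5%, the VQ rate is 0.105. The standard error is √[(0.2 × 0.8 + 0.105 × 0.895) / 199] = 0.0357. The chance of passing the upper test is Φ[(0.10 - 0.095) / 0.0357 - 1.645] = Φ(-1.505) ≈ 6.6%. The lower test is passed almost surely.

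**Exact enumeration of the plan's rule** (199 per arm, true exposure effect exactly 10 points), chance of declaring equivalence:

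| Assumed rates | c = 0% | c = 3% | c = 5% |
|---|---|---|---|
| 20% vs 10% | 5.3% | 6.2% | 6.9% |
| 15% vs 5% | 5.6% | 6.8% | 7.7% |
| 27% vs 17% | 5.0% | 5.8% | 6.3% |

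If crossover reached 10%, above anything the documents expect, the first row would give 8.9%.

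**Large effects.** With the preliminary rates of 32% and 6%, 5% crossover leaves 0.95 × 26 = 24.7 points, and a false equivalence finding is essentially impossible. The issue is confined to true effects near the margin.

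**Cost of a correction.** Dividing the difference and its standard error by (1 - c) is the same as testing the as-randomised difference against 10 × 0.95 = 9.5 points at c = 5%. It brings the error back to about 5.0-5.6% in the three scenarios. If it were a mandatory second test, power to show equivalence at equal 15% rates would fall from 75% to 69% at 5% crossover.

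**The case against.** The best defence is that the plan tests what it defines. The two rates in the hypothesis are those of the CTPA and VQ groups as assigned. CTPA after a non-diagnostic VQ is part of the VQ pathway in section 6.0, and limiting exposure is a question about strategy. For that comparison the as-randomised test keeps its stated error rate. This stands: the as-randomised choice is not a mistake. It does not cover the exposure claims in section 1.2.

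The second defence is size. The documents support 3% to 5% crossover, and there the inflation is about 1 to 2 points. This also stands. There is some reason for caution about the forecast. The 3% comes from 100 retrospective patients who had already been selected for VQ. Section 2.1 also speaks of a normal chest radiograph, while the exclusion criteria in section 4.3 admit some abnormal ones. That is a reason to have the analysis ready, not evidence that crossover will be high.

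A reader might infer from section 4.5 that the analysis set contradicts the as-randomised rule. The documents do not show that. Section 4.5 defines enrolment, and section 2.1 says how patients are grouped, not that everyone randomised is analysed. A patient who has VQ and then CTPA has completed the assigned study and stays in the VQ group. If section 4.5 did limit the set, it would drop VQ-assigned patients who went straight to CTPA, which would lessen the dilution. What remains is an ambiguity.

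**Conclusion.** The point holds as a modest gap. For conclusions about contrast exposure, the only planned analysis leans towards equivalence, and nothing in the plan lets a reader see by how much. At 3% to 5% crossover, the chance of a false equivalence finding at a true 10-point effect is about 6% to 8% instead of about 5%. These figures rest on assumed arm rates, 199 evaluable patients per arm, and crossover unrelated to AKI risk. The Appendix 1 flowchart could not be seen.

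A reader might go further and infer that the primary test is invalid, or that a false equivalence result is likely. The documents do not support either: the strategy comparison is sound, the expected crossover is low, and the bias matters only near the margin. Error rates well above these need crossover of 10% or more, which no section anticipates.

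**What to change.** Keep the as-randomised equivalence test as primary. In section 2.1, pre-specify one supportive exposure analysis of the primary endpoint, for example a complier-average risk difference: the as-randomised difference divided by one minus the crossover fraction, with its 90% confidence interval. Report it beside the primary result with the observed crossover rate, and state in advance that any claim of no effect of contrast will be qualified if the interval extends beyond 10 points in either direction.

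Add a sentence saying whether randomised patients who do not complete the assigned imaging remain in the analysis set, so that sections 2.1 and 4.5 agree.

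The cost is one extra analysis and a less favourable interval. It needs a variable for the imaging actually received. The enrolment data list in section 5.1 does not name one, but the planned record reviews should recover it. A formal second gate is not required: the fall in equivalence power from 75% to 69% shown above is a debatable price for correcting a bias of this size.
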